4.1 Primary and Secondary Outcomes

4.1.1 Primary outcomes

To evaluate the effect of BTEI gauze primary bleeding cessation after molar extraction.

4.1.2 Secondary Outcomes

To identify the adverse effect of using BTEI gauze and PVI gauze

4.2 Analysis Population

After randomization, there was no dropouts, Intent-to-Treat (ITT) and Per Protocol (PP) population were identical which was 44 participants, 22 participants for each group.

4.3 Statistical Methods

The demographic details of the participants were analysed using IBM SPSS Statistics version 26. The primary bleeding cessation time at post-extraction site after using BTEI gauze and PVI gauze was assessed at 2,5 and 7minutes post-extraction and recorded using categorical method. The proportion of participants in each group achieving haemostasis at each time point will be compared using Chi-square test. A two-tailed p-value of less than 0.05 will be considered statistically significant. The assumption for the Chi-square test will be assessed prior to analysis.

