**Evaluation of the Effect of Black Tea Extract on the
Primary Bleeding Cessation after Molar Extraction:
A Randomized Controlled Trial**

NCT number: NCT06687824

Date: 1/5/2025

1. Study Objectives

1.1 General Objectives:

To evaluate the effect of black tea extract on bleeding cessation after molar extraction

1.2 Specific Objectives:

- a) To determine the bleeding cessation time with used of normal sterile gauze with 0.5% povidone iodine (PVI)after molar extraction.
- b) To determine the bleeding cessation time with used of black tea extract-impregnated (BTEI) sterile gauze after molar extraction.
- c) To identify adverse effect of BTEI sterile gauze and PVI sterile gauze on post-extraction sites.
- d) To compare the bleeding cessation with used of the BTEI sterile gauze and PVI sterile gauze on post-extraction area.

2. Research Hypotheses

There is no difference of bleeding cessation time between BTEI gauze and 0.5% PVI sterile gauze.

3. Methodology

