3.3 Study Design and Intervention

This is a randomized controlled trial performed in Manipal University College Malaysia's (MUCM) Oral and Maxillofacial department (OMFS), from April to December 2024. The study protocol was approved Research Ethics Committee of MUCM (MUCM/ Research Ethics Committee- 042/2023). The trial is registered with National Clinical Trial Network with registration number NCT06687824. Informed consent from all participants was collected prior commencement of study. After selection of patient according to inclusion criteria and exclusion criteria, the demographic details (age, gender) of participants were recorded. Participants that are sensitive to black tea, use of complementary medical methods within the past month, having history of exposure of surgery site to radiation and use of antibiotic, corticosteroid, anticoagulant and contraceptive drug over the past month were excluded from the study. After exclusion of participants, we included participants that were age ≥ 18 years old and included in American Society of Anaesthesiologist (ASA) I and II. Those who met the inclusion and exclusion criteria were randomly selected and allocated into Group A and Group B using block randomization with block size 4.

After patient selection and allocation, the extraction site was anaesthetized with mepivacaine hydrochloride 2% / adrenaline 1:100,000 and molar was extracted with simple

extraction without odontotomy, flap incision, flap elevation and bone removal. Time of extraction was within 20 minutes. After irrigating the socket with 0.5% povidone iodine solution, BTEI gauze was applied for intervention group and PVI gauze for control group. The primary bleeding cessation state was evaluated at 2, 5 and 7 minutes. The result was investigated and recorded as <2, 2-5, 6-7 and > 7 minutes. When the bleeding stopped, the participant was discharged and a new gauze was given and participant was instructed to bite the gauze for 1 hour. 3 days later, all participants were contacted for follow-up assessment via phone to evaluate the presence of adverse effect in all participants.

4. Statistical Analysis Plan (SAP)

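### One primary hypothesis is tested by three unadjusted Chi-square tests (2, 5 and 7 minutes) with no rule for combining them, so its false-positive rate is undefined and can exceed 5%

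*Combined protocol and SAP*

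**What the plan says.** - **Hypothesis (section 2).** There is one null: "There is no difference of bleeding cessation time between BTEI gauze and 0.5% PVI sterile gauze".
- **Primary outcome (section 4.1.1).** It reads "To evaluate the effect of BTEI gauze primary bleeding cessation after molar extraction". It gives no time point and no summary measure.
- **Data (section 3.3).** The socket is checked at 2, 5 and 7 minutes, and each participant falls in one of four ordered categories: "The result was investigated and recorded as <2, 2-5, 6-7 and > 7 minutes".
- **Analysis (section 4.3).** "The proportion of participants in each group achieving haemostasis at each time point will be compared using Chi-square test". The threshold is single: "A two-tailed p-value of less than 0.05 will be considered statistically significant". On sparse data the plan says only: "The assumption for the Chi-square test will be assessed prior to analysis".
- **Timing.** The title block is dated 1/5/2025. Section 3.3 places the study "from April to December 2024", and section 4.2 already reports that "After randomization, there was no dropouts", with 22 participants per group.

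**The concern.** A 0.05 threshold fixes the error rate of one test. Here three tests address one claim, and the plan does not say which of them decides it. If success at any one time point counts as an effect, the chance of a false claim rises above that of a single test. If all three must succeed, it falls far below 5%. The plan fits either rule.

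The test itself is also open. The Chi-square assumption is to be assessed, but nothing is said about what follows if it fails. With 44 participants that will be common at the early and late time points, so the missing fallback is part of the primary analysis.

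This is the trial's only between-arm efficacy analysis, so its conclusion rests on the missing rule. The document post-dates the study period and does not say whether the analysis was fixed before outcomes were seen. Nothing in it shows that a result was selected. A stated rule with a stated date would settle the question, and neither is given.

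**Working it through.** The plan gives no overall error rate, expected proportions or power calculation, so there is no figure of its own to reproduce beyond the 0.05 threshold.

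**Inputs from the document.** n = 22 per arm (section 4.2); three time points and four ordered categories (section 3.3); two-sided 0.05 per test (section 4.3).

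**Assumed.** The category probabilities, because the document gives none. Patterns below are the percentages in <2 / 2–5 / 6–7 / >7 minutes.

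**Step 1: reference values.** Three independent tests would give 1 − 0.95³ = 1 − 0.857 = 14.3%. The upper bound under any dependence is 3 × 0.05 = 15%. The real tests are nested: haemostasis by 5 minutes includes haemostasis by 2 minutes. They are therefore positively correlated, and the true figure is lower and must be computed.

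**Step 2: the test at one time point.** Let a and b be the numbers with haemostasis by that time in the two arms, and t = a + b. The uncorrected statistic is

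X² = 44(a − b)² / [t(44 − t)], rejecting when p < 0.05 on 1 degree of freedom.

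The smallest expected count is min(t, 44 − t)/2. It is below 5 whenever fewer than 10 of the 44 participants have, or lack, haemostasis at that time.

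**Step 3: exact enumeration under no difference.** Each arm has 2,300 possible splits of 22 participants over four categories. All 2,300 × 2,300 pairs were weighted by their multinomial probabilities. This was done for all 969 patterns in 5% steps with every category at least 5%.

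| Decision rule and test | Minimum | Median | Maximum | Patterns above 5% |
|---|---|---|---|---|
| Any of three, uncorrected Chi-square | 6.6% | 11.0% | 13.6% (15/35/35/15) | 969 of 969 |
| Any of three, Fisher when an expected count is below 5 | 1.9% | 8.9% | 11.5% (25/25/25/25) | 97.5% |
| Any of three, no test when an expected count is below 5 | 0.06% | 7.5% | 10.9% | 83% |
| Any of three, Fisher throughout | 1.9% | 5.2% | 6.4% | 57% |
| Any of three, continuity-corrected throughout | 0.5% | 4.1% | 5.6% | 13% |
| All three required, uncorrected Chi-square | 0.0% | 0.2% | 2.0% | none |

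**Step 4: how often the Chi-square check fails.** Under 30/40/20/10 an expected count falls below 5 at 7 minutes in 99% of trials. Under 20/40/25/15 this happens in 62% at 2 minutes and 89% at 7 minutes.

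**Step 5: patterns outside the grid.** More concentrated outcomes give lower rates for any-of-three. For 80/15/4/1 it is 6.3% uncorrected and 3.9% with the Fisher fallback. For 90/8/1/1, 2/90/6/2 and 94/4/1/1 the uncorrected rates are 4.4%, 3.6% and 2.2%.

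**Step 6: the remedies on the same basis.** Under Holm the smallest p-value is judged at 0.05/3 = 0.0167. The chance of any rejection is then 0.5–4.8% with uncorrected Chi-square and 0.1–4.6% with the Fisher fallback, never above 5% on the grid. An exact Wilcoxon-Mann-Whitney test on the four categories, simulated with 60,000 trials in each of 11 patterns, gives 3.0–4.8%.

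**The case against.** **A single 2×4 Chi-square may be meant.** Section 4.3 describes a categorical record and names the test in the singular. Such a test on the same 969 patterns has an error rate of 1.3–5.0% (median 4.0%; empty categories dropped), so there would be no inflation. But section 4.3 compares proportions at each time point, which describes three 2×2 tables, and no overall test is mentioned. If one table was intended, section 4.3 still has to say so.

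**The largest figures ignore the planned assumption check.** This is fair. The uncorrected row applies Chi-square even where the check would fail. The rows that respect the check have lower maxima, 11.5% and 10.9%, but each depends on a fallback that the plan does not name. Fisher or a continuity correction throughout would keep the rate near nominal, at most 6.4% or 5.6%.

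**The excess is conditional.** This also stands. Every figure above 5% assumes that any one significant result counts, which the document does not state. That the uncorrected rate exceeds 5% in every pattern holds only on the grid; very concentrated outcomes fall below 5%. What is supported is that the rate is not fixed and can exceed 5%, not that it must.

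**An ordinal test changes the question.** It replaces proportions at set times with an overall shift in cessation time. That is closer to the hypothesis in section 2. Holm is the smaller edit for a team that wants to keep the three comparisons.

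**Conclusion.** The concern holds. Section 2 poses one question, section 4.3 answers it three times at an unadjusted 0.05, and nothing in the document turns three answers into one. With 22 per arm, the unstated choices move the false-positive rate of the primary claim from near zero (all three required) to 13.6% (any one, uncorrected Chi-square). With a Fisher fallback and any-one-of-three, it exceeds 5% in 97.5% of the patterns examined.

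These sizes rest on assumed category rates, on the any-one rule and on the 5% grid. The core finding needs none of them: there is no primary time point, combining rule, adjustment or sparse-table test. Because this is the only between-arm efficacy analysis, it must be fixed before a primary conclusion is drawn.

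**What to change.** Rewrite section 4.3 to name one confirmatory analysis.

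- **Preferred.** An exact Wilcoxon-Mann-Whitney test (or exact linear-by-linear trend test) on the four recorded categories, two-sided 0.05. Report the 2-, 5- and 7-minute proportions by arm with 95% confidence intervals as descriptive. Being exact, it needs no sparse-table rule.
- **Alternative A.** Keep the three tests and claim an effect only on Holm-adjusted p-values.
- **Alternative B.** Name one time point as primary and treat the other two as descriptive.

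Under A or B, also state the sparse-table rule, for example Fisher's exact test when any expected count is below 5. In every case, state whether the choice was made before the outcome data were seen, and label the analysis post hoc if it was not.

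**Cost.** One short paragraph and no new data. Under Holm, a nominal p between 0.0167 and 0.05 at a single time point would no longer support a claim on its own. As an illustration with assumed proportions of 50% and 90% at one time point, approximate power with 22 per arm falls from 85% at 0.05 to 71% at 0.0167. If outcomes had already been seen, no rewording restores confirmatory status, and the result has to be reported as post hoc whichever option is chosen.

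### Section 4.3 compares the arms only by chi-square p-values at three checks; no between-arm effect estimate or confidence interval is pre-specified

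*Combined protocol and SAP*

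**What the plan says.** Section 4.1.1 gives the primary outcome as "To evaluate the effect of BTEI gauze primary bleeding cessation after molar extraction". Specific objective (d) in section 1.2 is "To compare the bleeding cessation with used of the BTEI sterile gauze and PVI sterile gauze on post-extraction area". Section 2 puts forward the hypothesis that bleeding cessation time does not differ between the two gauzes.

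Section 3.3 describes the measurement: "The primary bleeding cessation state was evaluated at 2, 5 and 7 minutes", and "The result was investigated and recorded as <2, 2-5, 6-7 and > 7 minutes". Section 4.2 gives the analysis set as "44 participants, 22 participants for each group", with no dropouts.

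The only between-arm procedure is in section 4.3: "The proportion of participants in each group achieving haemostasis at each time point will be compared using Chi-square test". The decision rule follows: "A two-tailed p-value of less than 0.05 will be considered statistically significant". The section adds that the test's assumptions will be checked beforehand. It does not say whether a continuity correction applies or which test would replace the chi-square.

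**The concern.** A chi-square p-value addresses whether the proportions differ. It does not say by how much, or how precisely that is known. No section names a risk difference, risk ratio, odds ratio, difference in cessation time or any other between-arm measure, and none mentions a confidence interval. The trial sets out to evaluate an effect, but its plan does not commit to estimating one.

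The gap matters here because the trial is small and its stated hypothesis is one of no difference. If the p-value at a check is 0.05 or more, a reader given only that p-value could take the hypothesis as confirmed. An interval would show which differences the data leave open.

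**Working it through.** **Inputs.** From the documents: 22 per arm (4.2), two-tailed 0.05 (4.3), and a comparison of proportions at each of three checks (4.3). Assumed: all counts, because the documents give no haemostasis rates; the uncorrected Pearson test, because 4.3 names no variant; and the Newcombe interval as the illustration. The plan has no figure of its own to reproduce.

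**Formulas.** For a and b participants with haemostasis out of 22 in each arm:

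- Uncorrected chi-square = 44·(a(22−b) − b(22−a))² / (22·22·(a+b)·(44−a−b)), on 1 degree of freedom.
- Newcombe interval, with d = (a−b)/22, p₁ = a/22, p₂ = b/22 and Wilson limits (l, u) for each arm: lower limit d − √((p₁−l₁)² + (u₂−p₂)²), upper limit d + √((u₁−p₁)² + (p₂−l₂)²).

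**One case in full, 17/22 against 11/22.** Chi-square = 44·(17·11 − 11·5)² / (22·22·28·16) = 44·132²/216,832 = 3.54, so p = 0.060. The Wilson limits are 56.6% to 89.9% and 30.7% to 69.3%. The difference is 77.3 − 50.0 = 27.3 points. Lower limit: 27.3 − √(20.7² + 19.3²) = −1.0. Upper limit: 27.3 + √(12.6² + 19.3²) = 50.3.

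| Assumed counts | p (uncorrected) | Difference, points | Newcombe 95% CI |
|---|---|---|---|
| 11/22 vs 11/22 | 1.00 | 0 | −27.3 to 27.3 |
| 15/22 vs 11/22 | 0.22 | 18.2 | −10.2 to 42.9 |
| 17/22 vs 11/22 | 0.060 | 27.3 | −1.0 to 50.3 |
| 14/22 vs 8/22 | 0.070 | 27.3 | −2.0 to 50.8 |
| 18/22 vs 11/22 | 0.026 | 31.8 | 3.8 to 54.0 |

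**All possible results.** To avoid resting on chosen examples, take every ordered pair of counts from 0 to 22 (23 × 23 = 529) and note the interval limit farther from zero for each non-significant pair.

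| Set of pairs | Non-significant | Farther limit, points |
|---|---|---|
| All 529 | 229 | 14.9 to 50.8 |
| The 419 with every expected count at least 5 | 155 | 24.2 to 50.8 |

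The lowest value, 14.9, occurs when both arms have 0/22 or both have 22/22. The chi-square is undefined there, and these pairs are counted as non-significant. The value 24.2 occurs at 5/22 or 17/22 in both arms, and 50.8 at 8/22 vs 14/22. The largest observed gap that stays non-significant is 6/22 = 27.3 points.

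**Agreement between test and interval.** Among the 419 pairs, the uncorrected chi-square and the Newcombe interval never disagree. Over all pairs they disagree only at 0/22 vs 4/22, 18/22 vs 22/22 and their reversals (p = 0.036, CI −0.2 to 38.5, smallest expected count 2). With the Yates correction or Fisher's exact test, 24 of the 419 disagree; in each, the interval excludes zero while p is at least 0.05. For 18/22 vs 11/22 the uncorrected statistic is 44·154²/210,540 = 4.96 (p = 0.026). The Yates statistic is 44·(154−22)²/210,540 = 3.64 (p = 0.056).

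**The case against.** The strongest reply is that the effect is not hidden. The compared quantity in 4.3 is the proportion with haemostasis in each group, and 4.2 gives both denominators. Anyone shown the proportions could work out the difference and its interval, and the planned test remains valid. This stands: a reader might infer that the plan leaves the effect wholly unquantified or makes the test unsound, and the documents support neither. What remains is that no between-arm estimate or interval is pre-specified.

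Second, the 24-point floor depends on an expected-count rule that the plan does not state. Without known rates, proportions near 0% at 2 minutes or near 100% at 7 minutes cannot be ruled out. This also stands, so the general floor is about 15 points.

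Third, adding an interval creates a second inferential output that may conflict with the test. It would be tempting to say that this practically never happens, but that is true only of the uncorrected chi-square, which the plan does not specify. For the same reason, a blanket label of inconclusive for every p of 0.05 or more would not do, since under the other tests some such results have intervals that exclude zero.

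Finally, the documents do not say that a non-significant result will be read as no difference. Section 2 can be taken as an ordinary null hypothesis. The risk is one of misreading, which the plan does nothing to prevent.

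**Conclusion.** The concern holds as a gap in estimation and reporting. Section 4.3 plans p-values at 2, 5 and 7 minutes with implied per-arm proportions, and it pre-specifies no between-arm estimate or interval for an effect that the primary outcome sets out to evaluate.

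At 22 per arm, no non-significant uncorrected chi-square result rules out differences of 15 points or more in both directions, to rounding. Where all expected counts are at least 5, the figure is 24 points. Some non-significant results are compatible with up to 51 points. Significant results are imprecise too, as 18/22 vs 11/22 shows. These figures rest on assumed counts, the uncorrected test and the Newcombe method; the absence of a planned estimate does not. The change is worth making, though nothing here invalidates the planned test.

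**What to change.** In section 4.3, add:

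1. For each of the 2-, 5- and 7-minute checks, the number and proportion with haemostasis in each arm, and the between-arm difference in proportions with a 95% confidence interval (for example Newcombe).
2. A label that the intervals are unadjusted for three time points, and that these outputs were added after data collection. Section 3.3 places the trial "from April to December 2024", and the document is dated 1/5/2025.
3. A statement that a non-significant test will not be read as evidence of no difference, and that such a result will be interpreted from the interval.
4. The chi-square variant (with or without continuity correction) and the replacement test if the assumption check fails, with a statement that this test decides significance where it and the interval disagree.

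The cost is a few sentences and a few lines of output from data already recorded. The downsides are visibly wide intervals and, under the Yates correction or Fisher's exact test, some borderline disagreement with the interval (24 of the 419 pairs).
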